- OCT/ Optical Coherence Tomography
- ICDAS/ International Caries Detection and Assessment System
- UMN/ University of Minnesota
- SOD/School of Dentistry
- OHCRC/ Oral Health Clinical Research Center
- CTSI/ Clinical and Translational Science Institute

1.0 Objectives

The study aims to compare the short-term marginal integrity of two preparation techniques for Class I composite restoration using two visual assessment techniques, the FDI World Dental Federation and the US Public Health Service assessment criteria. In addition, Optical Coherence Tomography (OCT) will be used to assess the marginal integrity of the composite restoration.

2.0 Background

2.1 Research Question

A recent review of clinical studies published on the performance of posterior composite restorations that were recalled at least up to 24 months reported that the overall failure rate for studies conducted between 2006-2016 was 13.13% and the two main reasons for failure in these two decades remained the same, i.e. **secondary caries** (25.68% - 29.47%) and **composite fracture** (28.84% - 39.07%).¹ In *in vitro* studies, secondary caries has been attributed to interfacial gap or marginal defect both of which are consequences of polymerization contraction stresses. However, to date, **no clinical study** has been able to directly establish a link between these stresses (and its consequences) to secondary caries.²

World Dental Federation (FDI) and the United States Public Health Service (USPHS) clinical assessment criteria are the two main systems used to evaluate dental restorations in clinical trials. ^{3,4} Both systems are designed to evaluate different properties of a restoration and properties about marginal integrity have been reported to be the most frequent properties investigated of a resin composite restoration. The grading descriptions for these properties are subjective and the discrimination between grading and between properties (especially between marginal stains and secondary caries) is problematic. ⁵

Reasons for the lack of such a link are the discriminative deficiency of the clinical visual evaluation systems, the FDI and USPHS assessment criteria, and the ethical dilemma of restoration removal to assess for the presence or absence of secondary caries. It has been long acknowledged that an objective clinical measuring tool and new clinical study designs for secondary caries are needed to further the understanding of secondary caries initiation and progression and how these relate to the marginal integrity of dental restorations. This brings forth the need for a sensitive yet clinically applicable assessment method for interfacial debonding and demineralization.

Optical coherence tomography (OCT) is an optical, nondestructive, and clinically applicable technique that uses near-infrared waves to provide cross-sectional images of structures. It is regarded as a standard-of-care equipment in ophthalmology and its clinical application has recently expanded to cardiology and dermatology .^{6,7} In dentistry, it has been used intra-orally in clinical trials to detect and quantify enamel demineralization and to detect mucosal and submucosal lesions.⁸⁻¹¹ Optical coherence tomography and has been used to assess the performance of dental adhesives in a 12-month *in vivo* trial on non-carious cervical lesion¹². The authors reported that OCT outcome measures detected significant differences between groups while visual assessments did not. Hence supplementing the two visual assessment techniques with OCT outcome measures is expected to increase the sensitivity of short-term interfacial debonding and demineralization changes.

2.2 Preliminary Data

Figure 1 shows an unpublished *in vitro* 3D scan of a composite restoration placed at the cervical region of a tooth. The walls and floor of the restoration and defects inside the bulk of the restoration can be observed. The top view and various cross-sections (B-scans) of the 3D scan shown in Figure 1 are presented in Figure 2a and Figure 2b – 2d respectively.

Figure 1 : 3D render of a composite restoration placed at the cervical region of a tooth.

Figure 2: OCT scans of a composite restoration.

- (a) is an OCT *en face* view of a composite restoration showing the outline of the restoration.
 (b), (c) and
 (c) and (c) are OCT cross section views of the composite restoration.
- (b) No increased backscatter was observed at margin or the wall of the restoration.
- (c) Increased backscatter observed at the margin of the restoration (*) and at cavity floor (#)
- (d) Increased backscatter observed at the margin of the cavity (*) and cavity wall (#)
 - * indicates presence of demineralization and # indicates presence of debonding

2.3 Existing Literature

OCT, attached with a grip-type probe, has been used in dental clinical trials either to identify oral mucosal lesions or to qualitatively measure the extent of demineralization of dental caries.^{9,11,13} The capability of OCT in identifying and quantifying marginal defects and interfacial debonding around resin composite restorations has been demonstrated and verified *in vitro*. Park et al reported that OCT, when validated against light microscopy, detected 79.5% of the total gap lengths at the enamel interface.¹⁴ Bista et al reported a high correlation (r=0.96) between OCT and confocal microscopy measurements of sealed tooth-adhesive interface.¹⁵ Tabata et al demonstrated that SS-OCT can be used to detect enamel cracks at the margins of composite restorations noninvasively.¹⁶ It is worth noting too that it was also used to study the development of interfacial gap at the resin-tooth interface in real time. Thus, OCT outcome measures can provide objective and quantitative data for marginal gap and interfacial debonding and demineralization around dental composite restorations *in vivo*.

3.0 Study Outcome Measures

3.1 Primary Outcome Measures

The study's primary outcome measures include the following:

Evaluation and comparison of the short-term marginal integrity, up to 18-months, of two Class I composite preparation techniques using the FDI World Dental Federation and US Public Health Service criteria for marginal integrity of dental composite restorations.

Primary assessment endpoints

- 1. Marginal staining FDI³ and USPHS⁴ criteria
- 2. Marginal irregularities FDI³ and USPHS⁴ criteria

3.2 Secondary Outcome Measures

Evaluation and comparison of the short-term marginal integrity, up to 18-months, of two Class I composite preparation techniques using OCT backscattered intensity outcome measures for marginal integrity.

- 1. Elevated OCT reflectance of the occlusal cavosurface angle.
- 2. Elevated OCT reflectance along tooth-restoration interface.
- 3. Diminished OCT reflectance along tooth-restoration interface.

4.0 Study Interventions

The preparation will subsequently be followed with either of the following techniques:

4.1 Group 1

Lesion-specific cavity design with 90° cavosurface angle throughout the cavity margins.

4.2 Group 2

Lesion-specific cavity design with wide bevels throughout the cavity margins.

The cavity preparations in both groups were restored with a bulkfill resin composite (3M FiltekTM One Bulk Fill Restorative)

5.0 Study Population

Convenience sampling of 36 participants that meet study criteria and consent to participate in the study were recruited into the study. Please refer to Section 5.2 for participant recruitment and screening procedures. The participants were randomized into one of the two groups at the stage of restoration placement.

5.1 Inclusion Criteria:

Patient Level Inclusion Criteria

- 1. 18 years or older
- 2. Good general health
- 3. Fair oral hygiene
- 4. At least 20 teeth in occlusion
- 5. Available for the duration of the study

Tooth-level inclusion Criteria:

- 1. Participants with occlusal caries lesion/s in permanent posterior dentition except wisdom teeth
- 2. Caries lesion can be primary or secondary caries.
- 3. Caries lesion is in the International Caries Detection and Assessment System (ICDAS) 4 or 5 category.
- 4. The extent of the caries lesion bucco-lingually is likely not to exceed two-thirds of the occlusal table.
- 5. The selected tooth must be able to be isolated with either rubber dam or other isolation technique during clinical procedure.
- 6. The selected tooth must have an opposing antagonist.
- 7. The selected tooth should be periodontally healthy.

5.2 Exclusion Criteria:

Patient-level exclusion criteria:

1. Signs of bruxism

Tooth-level exclusion criteria:

- 1. Wisdom teeth
- 2. Present with irreversible pulpitis.
- 3. Periodontally compromised tooth that may require extraction.
- 4. Caries lesions that would require cuspal coverage.

6.0 Study Flow

6.1 Study Design

This study is a randomized single-blind clinical trial and followed the Consolidated Standards of Reporting Trials (CONSORT) statement.

Each participant received only one composite restoration and the participants were blinded to the type of preparation technique used. The study dentist who completed the restoration was not blinded to the preparation technique because the form (shape) of the two types of preparations is distinctly different. However, the restoration evaluators will be blinded to the preparation design.

A HIPAA-compliant and browser-based electronic capture software, REDCap, was used for consent taking and research data recording and storage, including intraoral digital photographs. All data remained within REDCap and access was restricted to authorized personnel only. OCT scans were de-identified prior to uploading into BOX storage and linked to data in REDCap through study participant ID.

6.2 Screening Procedures

A UMN CTSI data pull, housed in a data shelter, was generated as a random query. A preliminary data screening was conducted by the PI using the random order provided and a preliminary list of patients that satisfy the Patient- and Tooth-level inclusion criteria was created. The patients were contacted via telephone to invite them to be a part of the study. If interested, a telemeeting was scheduled with a trained team member.

The telemeetings were conducted via Zoom and study information was shared with the potential participants using Microsoft PowerPoint slides and any arising questions arising were answered. For participants who did not have access to the internet or were able to devise access, they were called on a phone line. At the end of this telemeeting, an in-person screening appointment was scheduled for interested participants, and a packet containing the combined consent/HIPAA form, Guidelines and Consent for Unsecured Email Correspondence for Research Participants, and the study instruction sheet were mailed to them either physically or electronically.

During the in-person screening, consent was attained from the participants. Participants were then screened to ensure that the patient-level inclusion criteria were still met, and the tooth indicated by the data pull for a Class I restoration was examined to ensure the tooth-level inclusion criteria were still met. A screening log was maintained in the data shelter. If both patient- and tooth-level inclusion criteria were still met, relevant medical history was obtained from the participants, a full-mouth dental examination was conducted and an optical impression of the teeth in the same quadrant of the tooth to be treated was taken with an intraoral 3D scanner.

From these optical impressions, customized guides for OCT scanning were designed and 3Dprinted for each participant. These scan guides ensured swift and accurate positioning of the OCT intraorally whereby the buccal, occlusal and lingual surfaces of the tooth are included in the 3D scans and the occlusal surface within the focal range of the OCT. The scan guides also minimized motion artifacts and enabled scanning of the teeth in the same orientation across all time points.

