6.3 Dental Restoration Procedure

Participants were randomized into one of two groups using a randomization module incorporated in REDCap. Participants and evaluators were blinded to the assignment, but the study dentist was not.

Prior to scanning with OCT, the participants were instructed to brush their teeth. The fit of the OCT scan guide was then checked and adjusted if needed. Once the scan guide was properly positioned on the tooth that required restoration, excess saliva was removed using pressurized air. Next, the OCT intraoral probe was inserted into place, and pre-operative 3D OCT scans of the tooth were conducted. The scan rate was 20KHz and the scans took approximately 3-5 seconds depending on the size of the tooth. Laser safety glasses were worn by the participant and the operator.

The restorations for both groups were placed by one study dentist. Pre-operative occlusal contacts on intercuspal position and lateral excursions were marked with an articulating film and recorded. Local anaesthesia was then administered, and quadrant isolation was achieved with rubber dam. The Selective Caries Removal method was used in all cases except for cases where caries encroaches into the inner third of dentin, whereby the Partial Caries Removal method was performed. The Partial Caries Removal method was followed by lining of the pulpal floor with a thin layer of Dycal as an indirect pulp-cap material and light-cured glass ionomer (3M Vitrebond).

The cavity preparations were subsequently followed with either of the following techniques:

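### Evaluator blinding is stated without exception, but the OCT outcomes are read where the two preparations differ, so the two significant baseline OCT results cannot be taken as blinded

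*Combined protocol and SAP*

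**What the plan says.** Two sections of the combined protocol and SAP deal with blinding. Section 6.1 exempts the study dentist "because the form (shape) of the two types of preparations is distinctly different" and then adds: "However, the restoration evaluators will be blinded to the preparation design". Section 6.3 says: "Participants and evaluators were blinded to the assignment, but the study dentist was not". Neither separates the visual examiners from whoever reads the OCT scans.

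Section 4.0 defines the arms by the margin. Group 1 is "Lesion-specific cavity design with 90° cavosurface angle throughout the cavity margins" and Group 2 is "Lesion-specific cavity design with wide bevels throughout the cavity margins". Both receive the same composite.

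Section 3.2 lists three OCT outcomes. The first is "Elevated OCT reflectance of the occlusal cavosurface angle". The second and third are elevated and diminished reflectance along the tooth-restoration interface. Of an example scan, section 2.2 says: "The walls and floor of the restoration and defects inside the bulk of the restoration can be observed".

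The only masking step described for the scans is that they were de-identified before upload (section 6.1). Section 9.2 names the tests used on the OCT data but not how reflectance was measured. Section 10.4 reports two significant OCT differences at baseline.

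**The concern.** The reason given for not blinding the dentist is that the shape of the preparation reveals the group. A finished composite surface may hide that shape from an examiner looking at the tooth. OCT images beneath the surface, so the same reason may apply to anyone reading the cross-sections. Removing the participant's identity from a file leaves the margin shape in the picture.

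This would matter less if reflectance were measured by a fixed rule that no reader could influence. The documents state no such rule: no intensity cut-off for elevated or diminished, no software, no number of readers, and no statement of who read the scans. Section 2.1 criticises visual grading as subjective, and section 2.3 offers OCT as the objective, quantitative alternative. That advantage depends on a measurement rule that is not described.

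At stake is how the only positive findings are read. Someone who carries the general blinding statement forward to section 10.4 would treat the Group 1 versus Group 2 differences as blinded comparisons, and the documents do not support that.

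**Working it through.** No formula settles this point, so the sections are set side by side. Arithmetic is used only to identify which results are affected and whether a size can be given.

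1. **Does the outcome location reveal the arm?**
   - Elevated reflectance at the cavosurface angle: the arms are defined by this same feature (section 4.0 against section 3.2). The link is direct.
   - Elevated and diminished reflectance along the interface: the arms are not defined by the interface, but the margin lies in the same cross-sections. The link is indirect.

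2. **Can OCT show the shape?** Section 2.2 describes walls and floor as visible, and its figure legend marks findings at the margin, wall and floor. The example is an in vitro cervical restoration. It shows that the technique can display cavity geometry. It does not show that a bevel was recognisable in these intraoral Class I scans. Hence probably, not certainly.

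3. **Is anything stated that would break the link?** De-identification (section 6.1) removes identity only. Sections 3.2, 6.3 to 6.5 and 9.2 give no masking of geometry, reading order, threshold or automated measurement.

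4. **Which results are affected?**
   - Marginal staining: no events, not tested (section 10.2).
   - USPHS irregularities: all scored A (section 10.3).
   - FDI irregularities: reported as P > 0.05 at each visit. Counts rebuilt from Table 6 for scores 1, 2a and 2b are as follows.
     - Baseline: 7, 8, 3 against 8, 6, 4.
     - 6 months: 12, 4, 0 against 12, 4, 1.
     - 18 months: 8, 6, 0 against 7, 4, 2.
     - Two-sided Mann-Whitney p is about 0.96, 0.73 and 0.64, which agrees with the report.
   - OCT at baseline (Table 7): elevated cavosurface reflectance 6.75 against 1.56, and elevated interface reflectance 16.20 against 7.44, both P < 0.05. Diminished interface reflectance is 14.44 against 18.75, reported as not significant.

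   The two elevated-reflectance outcomes are therefore the only significant differences reported. Both are secondary and given at baseline only.

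5. **Can a size be attached?** One could ask how large a reading shift would remove each difference, using a t-test on Table 7 read as mean ± SD with 18 per group. That approach fails two checks.
   - *Against the reported result.* For diminished reflectance, SE = √((4.36² + 4.29²)/18) = √(37.41/18) = 1.44, and t = (14.44 − 18.75)/1.44 = −2.99, p about 0.005. Section 10.4 reports no significant difference for this outcome.
   - *Against what is possible.* For a non-negative percentage with mean 1.56 and n = 18, the SD is largest when one value carries the whole total and the rest are zero. That gives 1.56 × √18 = 6.62. Table 7 prints 8.64.

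   Section 9.2 also says that the data were not normal and were compared by Mann-Whitney. No size is therefore derived.

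**The case against.** The strongest reply is that the blinding statement may cover only the visual examiners. Section 6.1 speaks of restoration evaluators. In sections 6.3 to 6.5 the restorations are evaluated by FDI and USPHS criteria, whereas an OCT scan is simply done. On that reading no false claim is made, and OCT blinding is just not addressed. This is a fair reading but not the only one: section 3.2 introduces the OCT outcomes as an evaluation and comparison, and section 6.3 says evaluators without restriction. Either way, the text does not support treating the OCT readings as blinded and needs to say so.

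Several stronger conclusions are tempting, and the documents do not support them.

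- *That OCT readings cannot be blinded.* This is inference. The remark that "the form (shape) of the two types of preparations is distinctly different" describes what the dentist cuts, not how a restored tooth looks on OCT. No section reports that a reader recognised an arm.
- *That a reader decided by eye what counted as elevated.* Section 3.2 calls these backscattered intensity measures. The method is unspecified, so subjective scoring is not established.
- *That the report presents the OCT results as blinded.* Section 10.4 does not mention blinding. The link comes only from the general statements in 6.1 and 6.3.
- *That the differences are produced by bias.* The third outcome comes from the same scans, was reported as non-significant, and is numerically higher in Group 2, whereas the two elevated outcomes are higher in Group 1.
- *That Table 7 shows how fragile the cavosurface result is.* The checks above rule this out.

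**Conclusion.** The point holds in limited form. As written, the blinding statement cannot be relied on for the OCT outcomes, and the two significant baseline differences in section 10.4 should not be read as blinded comparisons. The case is strongest for the cavosurface outcome and weaker for the interface outcome. Bias is possible and unquantified.

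The conclusion rests on two assumptions. The first is that a person, at some step, viewed cross-sections in which the margin shape could be seen. The second is that no reader-independent rule was applied, since none is stated. If the sponsor can document a fixed measurement rule or masked reading, most of the concern falls away once that is written down.

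The consequence is confined to secondary outcomes at one time point. It still affects what the trial can conclude, because no other reported comparison reached significance. The impossible SD and the mismatch for diminished reflectance in Table 7 are separate matters that need their own correction.

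**What to change.** 1. In sections 6.1 and 6.3, limit the blinding claim to the evaluators who scored the FDI and USPHS criteria.
2. In section 10.4, state that the OCT outcomes were not blinded to preparation shape and that the Group 1 versus Group 2 differences should be read with that caution. State who read the scans and how reflectance was measured. If a fixed rule was in fact used, give it.
3. Where the stored scans allow, re-measure them in random order with a fixed backscatter threshold set in advance, and lock the values before linking them to group. Report the result as the basis of Table 7 or as a sensitivity check on it.

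The first two changes cost a few sentences and make the blinding claim less favourable. The third needs no new visits but takes extra analysis work. It reduces dependence on the reader without removing it, because locating the interface may still need some judgement.

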6.3 Dental Restoration Procedure

Participants were randomized into one of two groups using a randomization module incorporated in REDCap. Participants and evaluators were blinded to the assignment, but the study dentist was not.

Prior to scanning with OCT, the participants were instructed to brush their teeth. The fit of the OCT scan guide was then checked and adjusted if needed. Once the scan guide was properly positioned on the tooth that required restoration, excess saliva was removed using pressurized air. Next, the OCT intraoral probe was inserted into place, and pre-operative 3D OCT scans of the tooth were conducted. The scan rate was 20KHz and the scans took approximately 3-5 seconds depending on the size of the tooth. Laser safety glasses were worn by the participant and the operator.

The restorations for both groups were placed by one study dentist. Pre-operative occlusal contacts on intercuspal position and lateral excursions were marked with an articulating film and recorded. Local anaesthesia was then administered, and quadrant isolation was achieved with rubber dam. The Selective Caries Removal method was used in all cases except for cases where caries encroaches into the inner third of dentin, whereby the Partial Caries Removal method was performed. The Partial Caries Removal method was followed by lining of the pulpal floor with a thin layer of Dycal as an indirect pulp-cap material and light-cured glass ionomer (3M Vitrebond).

The cavity preparations were subsequently followed with either of the following techniques:

Group 1 - Lesion-specific cavity design with 90° cavosurface angle throughout the cavity margins; Group 2 - Lesion-specific cavity design with wide bevel throughout the cavity margins was prepared. When cavity preparation is completed, the preparations in both groups were etched a 32% by weight phosphoric acid (3M ScotchbondTM Universal Etchant) on enamel and dentine for 15 seconds. After that, the etchant was rinsed away and an adhesive (3M ScotchbondTM Universal Adhesive) was applied on dentine and enamel with a microbrush for 20 seconds. The adhesive was light-cured for 10 sec with a curing light. Subsequently the preparation was restored in with a pre-warmed (using Bioclear Heatsync Kit) with a bulkfill resin composite (3M FiltekTM One Bulk Fill Restorative) and cured for 20 seconds according to the manufacturer's recommendation. The restorations were finished immediately with fine diamond burs and Sof-Lex XT coarse aluminum oxide disks (3M Oral Care). Polishing was carried out with the Sof-Lex Diamond Polishing System (3M Oral Care).

A post-operative 3D OCT scan of the restoration and the tooth was done using the same method as described above. Marginal integrity and staining of the restorations were evaluated using the FDI SQUACE criteria and the USPHS criteria. An intraoral digital photograph of the restoration was also taken.

